9.4 Dose Modification and Discontinuation

9.4.1 Adverse Drug Reactions (ADRs) Requiring Avelumab Discontinuation or Dose Modification

Any Grade 4 ADRs require treatment discontinuation with avelumab except for single laboratory values out of normal range that are unlikely related to study treatment as assessed by the investigator, do not have any clinical correlate, and resolve within 7 days with adequate medical management.

Any Grade 3 ADRs require treatment discontinuation with avelumab except for any of the following:

- Transient (\leq 6 hours) Grade 3 flu-like symptoms or fever, which are controlled with medical management
- Transient (\leq 24 hours) Grade 3 fatigue, local reactions, headache, nausea, emesis that resolves to Grade \leq 1
- Single laboratory values out of normal range (excluding Grade \geq 3 liver function test increase) that are unlikely related to study treatment according to the Investigator, do not have any clinical correlate, and resolve to Grade \leq 1 within 7 days with adequate medical management
- Tumor flare phenomenon defined as local pain, irritation, or rash localized at sites of known or suspected tumor

Any Grade 2 ADR should be managed as follows:

- If a Grade 2 ADR resolves to Grade \leq 1 by the last day of the current cycle, treatment may continue.
- If a Grade 2 ADR does not resolve to Grade \leq 1 by the last day of the current cycle, infusions should not be given on the following cycle. If at the end of the following cycle the event has not resolved to Grade 1, the subject should permanently discontinue treatment with avelumab (except for hormone insufficiencies, that can be managed by replacement therapy; for these hormone insufficiencies, up to 2 subsequent doses may be omitted).
- Upon the second occurrence of the same Grade 2 ADR (except for hormone insufficiencies that can be managed by replacement therapy) in the same subject, treatment with avelumab will be permanently discontinued.

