9.5 Management of Avelumab Immune-Related Adverse Events

Since inhibition of PD-L1 stimulates the immune system, immune-related AEs (irAEs) may occur. Treatment of irAEs is mainly dependent upon severity (NCI-CTC AE grade):

Grade 1 to 2: treat symptomatically or with moderate dose steroids, more frequent monitoring

Grade 1 to 2 (persistent): manage similar to high grade AE (Grade 3 to 4)

Grade 3 to 4: treat with high dose corticosteroids

Treatment of gastrointestinal, dermatological, pulmonary, hepatic and endocrine irAEs should follow guidelines set forth in the table below.

Gastrointestinal irAEs		
Severity of Diarrhea / Colitis (NCI-CTCAE v4.03)	Management	Follow-up
Grade 1 Diarrhea: < 4 stools/day over Baseline Colitis: asymptomatic	Continue avelumab therapy Symptomatic treatment (for example, loperamide)	Close monitoring for worsening symptoms Educate subject to report worsening immediately If worsens: Treat as Grade 2 or 3/4
Grade 2 Diarrhea: 4 to 6 stools per day over Baseline; IV fluids indicated < 24 hours; not interfering with ADL Colitis: abdominal pain; blood in stool	Delay avelumab therapy Symptomatic treatment	If improves to Grade 1: Resume avelumab therapy If persists > 5 to 7 days or recur: 0.5 to 1.0 mg/kg/day methylprednisolone or equivalent When symptoms improve to Grade 1, taper steroids over at least 1 month, consider prophylactic antibiotics for opportunistic infections, and resume avelumab therapy per protocol. If worsens or persists > 3 to 5 days with oral steroids: Treat as Grade 3 to 4

Grade 3 to 4 Diarrhea (Grade 3): \geq 7 stools per day over Baseline; incontinence; IV fluids \geq 24 hrs.; interfering with ADL Colitis (Grade 3): severe abdominal pain, medical intervention indicated, peritoneal signs Grade 4: life-threatening, perforation	Discontinue avelumab therapy per protocol 1.0 to 2.0 mg/kg/day methylprednisolone IV or equivalent Add prophylactic antibiotics for opportunistic infections Consider lower endoscopy	If improves: Continue steroids until Grade 1, then taper over at least 1 month If persists $>$ 3 to 5 days, or recurs after improvement: Add infliximab 5 mg/kg (if no contraindication), Note: Infliximab should not be used in cases of perforation or sepsis
Dermatological irAEs		
Grade of Rash (NCI-CTCAE v4)	Management	Follow-up

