Grade 2 AST or ALT > 3.0 to \leq 5 x ULN and / or total bilirubin > 1.5 to \leq 3 x ULN	Delay avelumab therapy Increase frequency of monitoring to every 3 days	If returns to Baseline: Resume routine monitoring, resume avelumab therapy If elevations persist > 5 to 7 days or worsen: 0.5 to 1 mg/kg/day methylprednisolone or oral equivalent and when LFT returns to Grade 1 or Baseline, taper steroids over at least 1 month, consider prophylactic antibiotics for opportunistic infections, and resume avelumab therapy
Grade 3 to 4 AST or ALT > 5 x ULN and / or total bilirubin > 3 x ULN	Discontinue avelumab therapy Increase frequency of monitoring to every 1 to 2 days 1.0 to 2.0 mg/kg/day methylprednisolone IV or IV equivalent Add prophylactic antibiotics for opportunistic infections Consult gastroenterologist Consider obtaining MRI/CT scan of liver and liver biopsy	If returns to Grade 2: Taper steroids over at least 1 month If does not improve in > 3 to 5 days, worsens or rebounds: Add mycophenolate mofetil 1 gram (g) twice daily If no response within an additional 3 to 5 days, consider other immunosuppressants per local guidelines

	if clinically warranted	
Endocrine ir AEs		
Endocrine Disorder	Management	Follow-up
Grade 1 or Grade 2 endocrinopathies (hypothyroidism, hyperthyroidism, adrenal insufficiency, type I diabetes mellitus)	
Continue avelumab therapy Endocrinology consult if needed
 
Start thyroid hormone replacement therapy (for hypothyroidism), anti-thyroid treatment (for hyperthyroidism), corticosteroids (for adrenal insufficiency) or insulin (for Type I diabetes mellitus) as appropriate.
 
Rule-out secondary endocrinopathies (i.e. hypopituitarism / hypophysitis)
	
Continue hormone replacement/suppression and monitoring of endocrine function as appropriate.

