10.3 At Every Cycle (+/- 3 days)

1. History and physical examination, including height, weight, vital signs (temperature, pulse rate, respiration rate, blood pressure), and performance status (Karnofsky)
2. Report side effects
3. CBC with differential and platelet count, CMP (including Na, Cl, BUN, Creatinine, K, CO₂, glucose, AST, ALT, alkaline phosphatase, total bilirubin, calcium, albumin, and total protein)
4. Treatment with avelumab
5. Free T4/TSH (every 4 cycles)

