11.1 TOXICITIES/SIDE EFFECTS

Expected toxicities from SBRT are highly dependent on location of the radiated lesion. Some of these toxicities may include fatigue, dermatitis, pneumonitis, esophagitis, chest wall pain, nausea, vomiting. In very rare cases, patients may experience brachial plexopathy, myelitis, bronchial damage, vascular damage, pericarditis, and/or hepatitis.

Primary toxicities of concern include radiation pneumonitis. Grade 2 and 3 pulmonary toxicity may be observed in 10% and 3% of patients, respectively. Other grade 2 –4 toxicities included chest wall pain in 20%, fatigue in 15-20%, esophagitis in 5-10%, and skin toxicity in 5-10% of patients. Inferior thoracic lesions may have an increased risk of liver, bowel, and kidney injury.

Possible short and long-term toxicities from avelumab include thyroid dysfunction requiring thyroid hormone replacement, adrenal crisis, liver function test abnormalities, pneumonitis, rash, diarrhea, and colitis. In a Phase 1b study of avelumab in patients with mesothelioma, treatment-related adverse events occurred in 41 of 53 patients (77.4%). The most common (>10%) were infusion-related reactions (20 [37.7%]), fatigue (8 [15.1%]), chills (8 [15.1%]), and pyrexia (6 [11.3%]), all of which were grades 1/2. Grade \geq 3 treatment-related adverse events occurred in 4 patients (7.5%). This included colitis, decreased lymphocytes, and increased GGT or CPK. There were no treatment-related deaths.

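### Section 9.4.1 makes an isolated, unrelated, transient liver-test rise stop avelumab at grade 3 but not at grade 4

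*Combined protocol and SAP*

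**What the plan says.** Section 9.4.1 sets mandatory stopping rules for avelumab by grade of adverse drug reaction.

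For grade 4 it says "Any Grade 4 ADRs require treatment discontinuation with avelumab except for single laboratory values out of normal range that are unlikely related to study treatment", with the remaining conditions "as assessed by the investigator, do not have any clinical correlate, and resolve within 7 days with adequate medical management".

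For grade 3, discontinuation is also the default, with four exceptions. The laboratory exception again concerns single out-of-range values, but a parenthesis removes liver tests at grade 3 or higher. The text runs on from that parenthesis as "liver function test increase) that are unlikely related to study treatment according to the Investigator", followed by the no-clinical-correlate condition and resolution to grade 1 or below within 7 days.

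Section 9.5 covers immune-related events and opens its table with "Treatment of gastrointestinal, dermatological, pulmonary, hepatic and endocrine irAEs should follow guidelines set forth in the table below". The row for grade 3 to 4 liver-test elevation is defined by "AST or ALT > 5 x ULN and / or total bilirubin > 3 x ULN", and its action begins "Discontinue avelumab therapy Increase frequency of monitoring to every 1 to 2 days".

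Section 13.1 requires permanent discontinuation for the reasons listed in Section 9. It adds intolerable events that dose modification or delay cannot manage, and it lets the treating physician stop the drug when that is best for the patient.

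**The concern.** A stopping rule should become stricter, or at least no looser, as severity rises. Here one class of laboratory event loses its mandatory stop on moving from grade 3 to grade 4.

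Liver function test abnormalities are among the possible avelumab toxicities listed in Section 11.1, so the class is relevant to this drug. The protocol also admits settings in which an investigator could reasonably attribute a rise to something other than avelumab. Section 6.2 allows patients with liver metastases to enter with AST and ALT up to 5 x ULN, and Section 11.1 notes a possible increase in liver injury risk when inferior thoracic lesions are irradiated. At grade 3 the liver-test exclusion takes that attribution judgement out of the decision. At grade 4 the judgement stays in.

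What is at stake is patient protection and consistent handling between treating physicians. The trial's inference is not affected.

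**Working it through.** No arithmetic decides this point. The check sets the two laboratory exceptions in Section 9.4.1 side by side, applies both to one case, and then looks for other text that would remove the difference.

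**Step 1. The two exceptions compared.**

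| Condition | Grade 3 exception | Grade 4 exception |
|---|---|---|
| Single out-of-range laboratory value | Required | Required |
| Judged unlikely related by the investigator | Required | Required |
| No clinical correlate | Required | Required |
| Resolution within 7 days | Required, to grade 1 or below | Required, no target grade stated |
| Liver-test rises of grade 3 or higher | Excluded from the exception | Not mentioned |

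**Step 2. One case under both rules.** Take a single liver-test rise, judged unlikely related, with no clinical correlate, back to grade 1 or below within 7 days.

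- At grade 3: the liver-test exclusion removes the laboratory exception. The other three exceptions cover transient flu-like symptoms or fever; transient fatigue, local reactions, headache, nausea or emesis; and tumor flare. None fits, so avelumab must stop.
- At grade 4: all the listed conditions are met and nothing excludes liver tests. Section 9.4.1 does not require a stop.

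The order of severity is reversed for this case.

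**Step 3. Does other text restore the stop at grade 4?**

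- *Section 9.5, hepatic row.* It stops avelumab at grades 3 and 4 alike, but the table is introduced as governing immune-related events, whereas the exception is for values judged unlikely related to treatment. If a site applied the row to every elevation, Section 9.5 would stop a patient whom Section 9.4.1 excuses, and the two sections would conflict.
- *Section 13.1.* Its reference to Section 9 imports the same rules. A value that resolves within 7 days is not an intolerable event that cannot be managed by delay. The best-interest clause is a permission.
- *Section 10.3.* The panel at each cycle includes "glucose, AST, ALT, alkaline phosphatase, total bilirubin, calcium, albumin, and total protein". That detects a rise but sets no dosing rule.
- *Section 17.3.1.* Hy's Law cases must be reported to the drug supplier as serious adverse events. That governs reporting only.

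**Step 4. Intended or omitted?** The exclusion in the grade 3 bullet is worded for grade 3 *or higher*, although the bullet deals only with grade 3 reactions. Section 9.5 handles grades 3 and 4 together for liver tests. No reason is given anywhere for being more lenient at grade 4. An omission in drafting is the likelier explanation.

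**Step 5. Size.** The documents give no rate for grade 4 liver-test rises judged unlikely related. The nearest figure is in Section 11.1: 4 of 53 patients in the earlier avelumab mesothelioma study had a treatment-related event of grade 3 or higher, 4/53 = 0.0755, stated as 7.5%. Of those events the protocol says "This included colitis, decreased lymphocytes, and increased GGT or CPK"; AST, ALT and bilirubin are not named. Because the events were treatment-related they would not qualify for the exception, so the figure does not estimate how often it would be used.

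**The case against.** The strongest reply is that Section 9, read as a whole, already gives the right answer. The wording for grade 3 or higher in the grade 3 bullet has no purpose unless it reaches grade 4. The hepatic row in Section 9.5 is triggered by numerical thresholds with no attribution step, whereas the protocol writes a rule-out step where it wants one, as for myocarditis and for other immune-related events. Section 13.1 then makes the Section 9 reasons binding.

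This supports the view of what was intended. It does not make the rule operate at grade 4: the exclusion sits only under the grade 3 rule, and the hepatic row stands in a table limited to immune-related events. At best there are two competing readings of a mandatory stop, which is itself a reason to correct the text.

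A second reply is that an event unlikely to be related is not an adverse drug reaction at all. The grade 3 bullet uses the same condition and still stops the drug for liver tests, so the protocol evidently treats such events as falling within Section 9.4.1.

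A third reply is that the affected set is very small and no path to harm is shown. This largely stands. The value must resolve within 7 days, dosing is every 2 weeks, the panel is repeated each cycle, nobody is obliged to continue, and the physician may always stop.

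Finally, the correction would withdraw avelumab from a patient whose rise was judged unrelated and has resolved, in a disease that the protocol describes as having no FDA-approved second-line treatment. That cost is real, but the protocol already accepts it at grade 3.

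**Conclusion.** The point holds. For an isolated liver-test rise meeting the listed conditions, Section 9.4.1 requires discontinuation at grade 3 and does not require it at grade 4.

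This rests on reading Section 9.4.1 literally, on events judged unlikely related being handled under that section, and on the Section 9.5 hepatic row applying only to immune-related events.

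The severity is minor. The exception removes a mandatory stop and does not compel further dosing. Its frequency cannot be estimated from the documents. No consequence is shown for the primary safety endpoint, for the limits of 3 or more events in 13 patients and 5 or more in 27, or for progression-free survival.

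**What to change.** In the grade 4 sentence of Section 9.4.1, insert the liver-test parenthesis from the grade 3 bullet directly after the reference to single out-of-range laboratory values. Leave the rest of the sentence as it stands. The difference in the resolution condition (grade 3 names a target of grade 1 or below, grade 4 does not) could be tidied in the same amendment, but it is a separate matter and this correction does not depend on it.

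The cost is one parenthesis, with no extra tests, visits or patients. The downside is that a rare patient with an unrelated, transient grade 4 liver-test rise would have to stop avelumab, as the protocol already requires at grade 3.

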9.4.2 Treatment Modification for Symptoms of Infusion-Related Reactions

NCI-CTCAE Grade	Treatment Modification for Study Drug
Grade 1 – mild Mild transient reaction; infusion interruption not indicated; intervention not indicated.	Decrease the study drug infusion rate by 50% and monitor closely for any worsening.
Grade 2 – moderate Therapy or infusion interruption indicated but responds promptly to symptomatic treatment (for example, antihistamines, NSAIDs, narcotics, IV fluids); prophylactic medications indicated for ≤ 24 hrs.	Stop study drug infusion. Resume infusion at 50% of previous rate once infusion-related reaction has resolved or decreased to at least Grade 1 in severity and monitor closely for any worsening.
Grade 3 or Grade 4 – severe or life-threatening Grade 3: Prolonged (for example, not rapidly responsive to symptomatic medication and/or brief interruption of infusion); recurrence of symptoms following initial improvement; hospitalization indicated for clinical sequelae. Grade 4: Life-threatening consequences; urgent intervention indicated.	Stop the study drug infusion immediately and disconnect infusion tubing from the subject. Subjects have to be withdrawn immediately from study drug treatment and must not receive any further study drug treatment.

IV = intravenous; NCI-CTCAE = National Cancer Institute-Common Terminology Criteria for Adverse Event; NSAIDs = nonsteroidal anti-inflammatory drugs.

Additional Modifications for Patients with Grade 2 Avelumab Infusion-Related Reactions: In the event of a Grade 2 infusion-related reaction that does not improve or worsens after implementation of the modifications indicated in Section 9.4.2 (including reducing the infusion rate by 50%), the investigator may consider treatment with corticosteroids, and the infusion should not be resumed for that cycle. At the next cycle, the investigator may consider the addition of H2-blocker antihistamines (e.g., famotidine or ranitidine), meperidine, or ibuprofen to the mandatory premedications. Prophylactic steroids are NOT permitted.

Management of Avelumab-related Severe Hypersensitivity Reactions and Flu-like Symptoms: Many mAb therapies can induce flu-like symptoms and hypersensitivity reactions, including impaired airway, decreased oxygen saturation (<92%), confusion, lethargy, hypotension, pale/clammy skin, and cyanosis. Avelumab should be administered in a setting that allows for immediate access to an intensive care unit or equivalent environment if required. Patients should be placed on monitors immediately and epinephrine injections and dexamethasone infusions should be available for immediate access.

For prophylaxis of flu-like symptoms, 25 mg indomethacin or comparable nonsteroidal anti-inflammatory drugs (NSAID) dose (e.g., ibuprofen 600 mg, naproxen sodium 500 mg)

may be administered at the investigator's discretion 2 hours before and 8 hours after the start of each dose of avelumab IV infusion. Alternative treatments for fever (e.g., paracetamol or ibuprofen) and rigors (e.g., meperidine) may be given to patients at the discretion of the investigator.

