14.0 BIOSTATISTICS

The primary endpoint, the safety of a combination of avelumab and SBRT, will be defined based on the rate of any grade 3 or higher non-hematologic toxicity within the first 3 months after SBRT (for the rest of the section this will be referred to as AE). A two-stage stopping rule will be used to protect patients' safety. If 3 or more among the first 13 patients develop AEs, then the trial will be stopped and declared unsafe. Otherwise, an additional 14 patients will be enrolled and treated. If, among the total 27 patients, 5 or more patients are observed to have AEs, then the trial will also be declared unsafe. This stopping rule has a power of 80% declaring the true AE rate of 0.1 or lower safe, and a type 1 error rate (alpha) of 5% declaring true AE rate of 0.3 or higher safe.

For secondary endpoints, the overall response and the irradiated lesion and non-irradiated lesion response rates (4 months from start date of the combined therapy) based on RECIST 1.1 response criteria will be summarized by sample proportions and their confidence intervals. PFS and OS will be evaluated by Kaplan-Meier method.

For the exploratory objectives, we will evaluate changes of T-cell infiltration and serum immunophenotype at baseline and after SBRT + immunotherapy both in- and outside the irradiated field. The former is measured as numerical values so we will use Wilcoxon signed-rank test. The latter is categorical so we will tabulate it and employ the marginal homogeneity test. Due to the expected small sample size, results will be interpreted cautiously. The imaging studies using DWI-MRI and DCE-MRI, and FDG-PET will be correlated with biopsy results by McNemar's tests.

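### Section 9.4.2 gives two opposite dosing instructions for a grade 2 infusion reaction that fails to improve, or that returns or worsens at half rate; the effect on the primary endpoint is secondary and probably small.

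*Combined protocol and SAP*

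**What the plan says.** The table in Section 9.4.2 separates grade 2 from grade 3 infusion reactions largely by how they respond.

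- **Grade 2:** "Therapy or infusion interruption indicated but responds promptly to symptomatic treatment". The infusion is stopped, and then: "Resume infusion at 50% of previous rate once infusion-related reaction has resolved or decreased to at least Grade 1 in severity".
- **Grade 3:** "Prolonged (for example, not rapidly responsive to symptomatic medication and/or brief interruption of infusion); recurrence of symptoms following initial improvement". For grades 3 and 4: "Subjects have to be withdrawn immediately from study drug treatment and must not receive any further study drug treatment".

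The paragraph on additional modifications, directly below the table, starts from this event: "In the event of a Grade 2 infusion-related reaction that does not improve or worsens after implementation of the modifications indicated in Section 9.4.2". It states that those modifications include the 50% rate reduction. Corticosteroids may be considered, the infusion is not restarted in that cycle, and extra premedication may be considered at the next one. The event is called grade 2 throughout.

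Section 14.0 defines the primary endpoint as "the rate of any grade 3 or higher non-hematologic toxicity within the first 3 months after SBRT". Infusion reactions are not excluded. The Section 1.0 summary ties this endpoint to CTCAE v4.0, and Section 11.1.1 requires CTCAE v4.0 grading for all adverse events.

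**The concern.** Prompt response is part of the table's definition of grade 2. A reaction that has failed to respond to the grade 2 measures, or has come back after them, is what the table describes as grade 3. An investigator who follows the paragraph would plan for another infusion. An investigator who follows the table would withdraw the patient from avelumab. Both could cite Section 9.4.2.

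The main stake is patient safety, and it arises at every infusion, including cycles 1 and 2. The secondary stake is the safety verdict. The limits are 3 of 13 and 5 of 27, so the grade given to one patient's reaction can matter if it falls in the counting window and the count stands just below a limit.

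**Working it through.** **1. The paragraph's cases set against the table**

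| Case within the paragraph | Table descriptor it meets | Table's instruction | Paragraph's instruction |
|---|---|---|---|
| No improvement after interruption and symptomatic treatment | Grade 3: not rapidly responsive | No further study drug | Skip the rest of this cycle; next cycle foreseen |
| Return or worsening after the restart at 50% rate | Grade 3: recurrence after initial improvement | No further study drug | Same |
| Persists at the reduced rate but settles promptly once treated, or worsens within grade 2 without recurrence | Can remain grade 2 | Grade 2 row | Same; no conflict |

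The second row is the clearest. The grade 2 row allows the half-rate restart only after the reaction has resolved or fallen to grade 1. Symptoms that come back after that restart therefore follow an initial improvement, whatever *promptly* means.

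Section 9.4.1 does not settle the matter. It stops avelumab for grade 3 reactions, with listed exceptions. For grade 2 it stops avelumab only if the reaction is unresolved after a skipped cycle, or on a second occurrence. Both rules depend on the grade in dispute.

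**2. The plan's own operating characteristics (Section 14.0)**

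The verdict is safe if at most 2 of the first 13 patients and at most 4 of all 27 have a primary AE:

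P(safe | p) = Σ(x = 0 to 2) Bin(x; 13, p) × P[Bin(14, p) ≤ 4 − x]

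- p = 0.10: 0.2542 × 0.9908 + 0.3672 × 0.9559 + 0.2448 × 0.8416 = 0.809 (plan: power 80%).
- p = 0.30: 0.0097 × 0.5842 + 0.0540 × 0.3552 + 0.1388 × 0.1608 = 0.047 (plan: alpha 5%).

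The design reproduces. At p = 0.10, the chance of exactly 2 of 13 is 0.245, and the chance of passing stage 1 and ending at exactly 4 of 27 is 0.114. At either count, one more counted patient would reverse the decision.

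**3. How many events could be affected**

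- The window starts at SBRT, which follows two avelumab cycles (Section 9.1.1). Only reactions from cycle 3 until 3 months after SBRT can count.
- Section 11.1 cites 20 infusion reactions among 53 patients (37.7%), all grade 1 or 2. That is 0 of 53 at grade 3 or higher. The exact upper 95% limit is 1 − 0.05^(1/53) = 5.5% one-sided, or 1 − 0.025^(1/53) = 6.7% two-sided, over all cycles.
- The documents give no rate for reactions that fail to improve or that recur. The shares below are assumptions.

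**4. Sensitivity**

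Let x be the share of patients with such an event in the window, independent of other AEs. If the other AE rate is 0.10 and the events are counted, the rate is 1 − 0.90(1 − x). If the true total is 0.30 and they are left uncounted, the counted rate is 1 − 0.70/(1 − x).

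| x (assumed) | Rate if counted, base 0.10 | P(safe) | Rate if uncounted, total 0.30 | P(safe) |
|---|---|---|---|---|
| 0 | 0.100 | 80.9% | 0.300 | 4.7% |
| 0.5% | 0.1045 | 78.7% | 0.2965 | 5.1% |
| 1% | 0.109 | 76.5% | 0.2929 | 5.5% |
| 2% | 0.118 | 71.9% | 0.2857 | 6.4% |
| 5% | 0.145 | 57.0% | 0.2632 | 10.1% |

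**The case against.** The paragraph is a dosing instruction and defines no grade. Its heading limits it to grade 2 reactions, and nothing in it overrides the mandatory grade 3 row. A reaction that meets the grade 3 descriptor should be recorded as grade 3 under CTCAE v4.0 and counted, whatever was done with the infusion. Next-cycle dosing is only implied, and some reactions the paragraph covers can properly stay grade 2.

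Most of this stands as a limit on the endpoint effect. A reader might infer that choosing between paragraph and table freely decides the safety verdict, or that a large share of patients is affected. The documents do not support either reading. Grading is already tied to CTCAE v4.0, and cycles 1 and 2 lie outside the window. A share such as 10% in the window exceeds the 6.7% upper limit from the cited cohort over all cycles. A reader might also infer that everything in the paragraph is grade 3, or that it orders re-treatment; it does neither.

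The objection does not remove the conflict for the first two cases in the table above. The paragraph's stated trigger is failure of the grade 2 measures, so it is written for events that largely meet the grade 3 descriptors, and its premedication advice has no purpose unless avelumab is given again. Leaving *promptly*, *rapidly* and *brief* undefined makes some reactions a matter of judgement, but that does not reconcile two instructions.

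**Conclusion.** Section 9.4.2 contradicts itself for part of the additional-modifications paragraph. A reaction that does not improve after interruption and treatment, or that returns or worsens after the half-rate restart, is grade 3 by the table, where the subject "must not receive any further study drug treatment". The paragraph calls the same event grade 2 and foresees another cycle. This rests on the text alone and needs no assumed rate.

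The endpoint effect is secondary and probably small. At an assumed 0.5% to 1% of patients, the chance of a safe verdict moves by about 2 to 4 percentage points at a base rate of 0.10, and by less than 1 point at a true total of 0.30. The 5% row is close to the one-sided limit from the cited cohort and is best read as an upper case. If no such event falls in the window, there is no effect. Which dosing instruction is right is a clinical matter, and this review takes no position on it.

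**What to change.** Reconcile the additional-modifications paragraph of Section 9.4.2 with the grade 2 and grade 3 rows, so that a reaction that fails to improve, returns or worsens has one grade and one dosing instruction. The sponsor's clinicians decide which.

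Optionally, add a cross-reference in Section 14.0 saying that the grade used for the primary endpoint is the one given by the CTCAE descriptors, whatever dosing action was taken. This repeats what Sections 1.0 and 11.1.1 already imply, but it puts the rule beside the stopping limits.

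The cost is one revised paragraph and at most one sentence. Sample size, limits and visits do not change. A few reactions may be recorded at a higher grade than an investigator would otherwise have chosen.
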